## 2.4 RISK/BENEFIT ASSESSMENT

### 2.4.1 KNOWN POTENTIAL RISKS

There is a limited potential for risks associated with phlebotomy, a commonly performed procedure that will be performed exclusively by individuals specially trained in this procedure. Standard phlebotomy techniques to minimize venipuncture side effects (hand hygiene, glove use, skin antisepsis, and the use of sterile, single-use needles will minimize the risk of infection; appropriate angle of needle entry to avoid hematoma, application of pressure for 3-5 minutes after drawing blood). There is a risk of discomfort, bleeding which is generally mild, bruising, and a remote risk of infection that will be minimized by using these techniques

### 2.4.2 KNOWN POTENTIAL BENEFITS

Subjects enrolled in this study will not derive direct benefit. Data from this study may help inform future studies or provide information for individualized therapy.

## 3 OBJECTIVES AND ENDPOINTS

The primary objective of the study is to determine whether platelet expression of FcγRIIa is associated with risk of MI, stroke, and death.

Secondary objectives are

- Develop a score that combines clinical characteristics plus platelet expression of FcγRIIa to determine the risk of MI, stroke, and death.
- Determine whether platelet expression of FcγRIIa is associated with risk of major bleeding.

The primary endpoint is the composite of death, MI, and stroke. A secondary endpoint is clinically significant bleeding according to BARC type 2-5.

## 4 STUDY DESIGN

### 4.1 OVERALL DESIGN

This is a prospective, observational multicenter non-interventional cohort study designed to integrate into the regular standard of care (Figure 5, Schematic Overview). Subjects who are admitted to the hospital with an MI will be screened. Screening will entail review of the medical

record for selected entry criteria. If the subject meets entry criteria, written informed consent will be obtained. Subjects will be enrolled into the study (called Day 1) before discharge from a hospitalization for a confirmed type 1 MI (STEMI or non-STEMI), referred to as the index event. Subjects will not have their care altered by participation in the study; subjects' medical regimens will be determined by their health care provider. Enrollment of subjects who are receiving anticoagulants for atrial fibrillation or venous thromboembolic disease will be limited to approximately 100 subjects.

[figure not shown]
After informed consent is obtained and the subject eligibility is confirmed, each subject will be assigned a unique identifier. Clinical characteristics and biochemical results will be associated with the unique identifier. The association between the subject's identity and the unique identifier will be kept in a secure file. Clinical characteristics will be recorded and blood (approximately 3 ml to 6 ml) will be obtained for analysis of platelet FcγRIIa expression. Blood can be taken up to 2 weeks post-study enrollment. The samples for platelet FcγRIIa expression will be assayed by a core laboratory to ensure standardization.

Subjects will be contacted by telephone every 6 months and asked a standardized set of questions to determine whether they have had a cardiovascular event (MI, stroke), bleeding event or have died. At each study visit, subjects will be queried about their medications with a specific focus on their anti-thrombotic regimen. Changes to their anti-thrombotic regimen will be documented in association with the time when changes were made. All subjects will be contacted at the end of the study for a final telephone visit. Medical records will be reviewed to confirm subject reported endpoints.

The primary endpoint will be the composite of death, MI, and stroke. MI will be defined in accordance with the 4th universal definition (Thygesen 2018) and stroke consistent with consensus guidelines (Sacco 2013). The incidence of clinically significant bleeding will be determined using the Bleeding Academic Research Consortium (BARC) scale (Mehran 2011) and is defined as BARC type 2-5. Study endpoint events will be confirmed by the review of medical records by the investigator and all relevant medical records will be obtained by the site for submission to the sponsor (as described in Section 10.8). Subjects who experience an endpoint event will continue to be followed throughout the entire study and any subsequent endpoint events will also be confirmed and recorded. See Appendix 1 for study endpoint event definitions.

A total of approximately 800 subjects will be enrolled at approximately 10-20 sites in the US. It is anticipated that it will take about 12 months to enroll the total number of subjects. The study and subject follow-up will continue until 1) at least 80 ischemic events (MI, stroke, and death) have occurred, and 2) the last subject enrolled has completed at least 18 months of follow-up. Based on an annual ischemic event rate of 10%, the overall length of participation in the study is anticipated to be up to 3 years. Results will be monitored during the course of the study.

Figure 5 Schematic Overview of the Study

MI=myocardial infarction; NSTEMI= non-ST-segment elevation MI, STEMI= ST-segment elevation MI

\* Subjects who experience an endpoint event will continue to be followed throughout the entire study and any subsequent events will also be confirmed and recorded.

#### 4.2 END OF STUDY DEFINITION

The study will be stopped when 1) at least 80 ischemic events (MI, stroke, and death) have been confirmed and 2) the last subject enrolled has completed at least 18 months of follow-up. The study will be considered complete once all subjects have had their last telephone visit.

#### 4.3 SUBSTUDY

Platelet function tests exhibit substantial intra-individual variability when measures are repeated 2 to 6 weeks after initial testing (Frelinger 2013, Hochholzer 2014, Nührenberg 2015). Results from a study in healthy subjects suggest that FcγRIIa will vary by <10% over the course of 2 to 6 weeks (McMahon 2019).

The objective of the substudy is to demonstrate that the FcγRIIa assay provides a consistent measure of platelet expression of FcγRIIa by measuring a second blood sample after study enrollment and the first/baseline blood sample is taken. The substudy endpoint is the measurement of platelet expression of FcγRIIa 2 to 6 weeks after study enrollment.

The substudy will be performed at some sites identified by early study start-up and prior experience in similar studies. Subjects enrolled in the parent study are eligible for the substudy. A second sample of blood will be obtained by phlebotomy 2 to 6 weeks after the subject is enrolled in the study. The results from this second sample of blood will be compared to FcγRIIa results from the first/baseline blood sample.

See Section 2.4 for the risk/benefit assessment associated with phlebotomy and the second blood draw.

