## 1.3 SCHEDULE OF ACTIVITIES

Procedures	Day 1 (prior to or on day of hospital discharge) a	Week 2 to Week 6 after study enrollment	Telephone Study Visit every 6 months (+/- 4 weeks)	Final Telephone Study Visit (+ 2 weeks after at least 80 ischemic events accrued)
Informed Consent	X			
Inclusion/Exclusion Criteria	X			
Clinical Characteristics	X			
Enrollment	X			
Anti-thrombotic Medication Review	X		X	X
Blood Sample to Quantify FcγRIIa b	X	X d		
Assess for Study Endpoints c			X	X
Complete Case Report Forms (CRFs)	X		X	X
	
a: Procedures can be done at any time after confirmation of myocardial infarction index event and prior to hospital discharge. Day 1 is defined as the day the subject is enrolled into the study and must occur prior to or on the day of hospital discharge.
 
b: Approximately 3 ml to 6 ml blood sample. Blood can be taken up to 2 weeks post-study enrollment.
 
c: Endpoints include Ischemic events (MI, stroke, death) and clinically significant bleeding BARC type 2-5.
 
d: For sites participating in the substudy, a 3 ml to 6 ml blood sample will be drawn 2 to 6 weeks after enrollment into the study
			

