## 8 STUDY ASSESSMENTS AND PROCEDURES

### 8.1 EFFICACY AND SAFETY ASSESSMENTS

This is an observational non-interventional study, therefore there is no evaluation of efficacy or safety. Blood will be taken prior to discharge from the hospital for the index MI event (see separate Laboratory Sample Manual for details on sample collection, storage, and shipment to a core laboratory) and will be used to quantify FcγRIIa. Blood can be taken up to 2 weeks post-study enrollment. Risks associated with phlebotomy include discomfort, bleeding, and a remote risk of infection.

Subjects will receive medications as determined by their health care provider and as part of regular standard of care. Subjects will be followed throughout the duration of the study to assess for study endpoints including MI, stroke, death, and bleeding events (BARC type 2-5). Subjects who experience an endpoint event will continue to be followed throughout the entire study and any subsequent events will also be confirmed and recorded.

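### Both substudy sampling windows start at enrolment and meet at day 14, so paired samples may be 0 to 42 days apart and repeatability over 2 to 6 weeks may be overstated

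*Protocol*

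**What the plan says.** **Second sample.** Protocol 4.3 states: "A second sample of blood will be obtained by phlebotomy 2 to 6 weeks after the subject is enrolled in the study". Note d to the schedule in Protocol 1.3 uses the same starting point ("blood sample will be drawn 2 to 6 weeks after enrollment into the study"), as does the synopsis in 1.1.

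**First sample.** Protocol 8.1 gives the default: "Blood will be taken prior to discharge from the hospital for the index MI event". The schedule in 1.3 puts this draw in the Day 1 column, and note a makes Day 1 the enrolment date, no later than discharge. Sections 1.3 (note b), 4.1 and 8.1 then allow a later draw: "Blood can be taken up to 2 weeks post-study enrollment".

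**Order and eligibility.** Protocol 4.3 describes the comparison as made "by measuring a second blood sample after study enrollment and the first/baseline blood sample is taken". This puts the second sample after the first but sets no minimum time between them. Any subject enrolled in the parent study is eligible, whatever the date of the first draw.

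**The interval of interest.** Protocol 4.3 contrasts FcγRIIa with platelet function tests, which vary "when measures are repeated 2 to 6 weeks after initial testing", and cites healthy-subject data suggesting that FcγRIIa "will vary by <10% over the course of 2 to 6 weeks". The first of these is explicitly an interval from test to test.

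**Analysis.** Protocol 9.4.7 leaves the substudy analysis to the SAP. SAP 5.1 to 5.10, the part available for this review, contains no substudy analysis, no minimum gap and no handling by actual draw date. Parts of the SAP were not available, so this does not show that such text is absent.

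**The concern.** The substudy is meant to show that one FcγRIIa measurement represents a subject over several weeks. That stability is one of the advantages over platelet function tests claimed in Protocol 2.2 and 2.3. The question concerns the time between two samples, but the protocol controls only the time of each sample from enrolment. Once the first draw can move, the gap is no longer controlled.

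A pair taken a few days apart says little about change over 2 to 6 weeks. Protocol 2.3 argues that expression is set when the platelet is produced and should hold for the platelet's life. On that reasoning, closely spaced draws partly sample the same platelets and mostly reflect measurement error. Including such pairs can only pull the estimated variability towards the result the substudy hopes to show. What is at stake is the substudy's conclusion. Neither the primary nor the secondary objectives depend on it.

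**Working it through.** The documents give no substudy sample size, agreement statistic or variability limit, so there is no planned figure to reproduce. The check is interval arithmetic, followed by a labelled illustration.

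**Inputs from the protocol** (enrolment counted as day 0; the choice of origin does not affect gaps)
- First sample: day 0 to day 14 (1.3 note b, 4.1, 8.1).
- Second sample: day 14 to day 42 (1.1, 1.3 note d, 4.3).

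**Permitted gap**
- Shortest = earliest second − latest first = 14 − 14 = 0 days.
- Longest = latest second − earliest first = 42 − 0 = 42 days.
- First sample on day 0: gap 14 to 42 days.
- First sample on day 14: gap 14 − 14 = 0 to 42 − 14 = 28 days.
- Window counted from the first sample instead: 14 to 42 days for every pair.

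Zero is the boundary case, with both draws on day 14.

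**Illustration: how many pairs fall under 14 days.** Assume second draws are uniform over days 14 to 42, a span of 28 days, and a share p of first draws is late.
- If late draws are uniform over days 0 to 14, a first draw on day a gives a gap under 14 days with probability a/28. This averages 7/28, so the share of pairs is 0.25p.
- If late draws all fall on day 14, the probability is 14/28, so the share is 0.50p.

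**Illustration: apparent within-subject CV.** Assume CV² = 1.9² + 10² × mean of (1 − exp(−gap/τ)), in percent. The 1.9 is the intra-assay CV from Table 1 in Protocol 2.3. The long-run biological CV of 10% and the time constant τ are assumptions. Two cases at τ = 10 days:
- None late (gap uniform 14 to 42): mean exp(−gap/10) = (10/28)(e^−1.4 − e^−4.2) = 0.0827; CV = √(3.61 + 91.73) = 9.76%.
- All on day 14 (gap uniform 0 to 28): mean = (10/28)(1 − e^−2.8) = 0.3354; CV = √(3.61 + 66.46) = 8.37%.

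In the table, the first figure in each range takes late draws as uniform over days 0 to 14, and the second puts them all on day 14. CVs were simulated with 1,000,000 pairs.

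| Late first draws | Pairs under 14 days | CV, τ = 3 d | CV, τ = 10 d | CV, τ = 30 d |
|---|---|---|---|---|
| 0% | 0% | 10.17% | 9.76% | 7.93% |
| 10% | 2.5–5% | 10.16–10.12% | 9.71–9.63% | 7.86–7.77% |
| 25% | 6.25–12.5% | 10.15–10.04% | 9.64–9.43% | 7.75–7.54% |
| 50% | 12.5–25% | 10.12–9.91% | 9.51–9.09% | 7.57–7.12% |
| 100% | 25–50% | 10.07–9.64% | 9.25–8.37% | 7.19–6.21% |

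The 0% row is also what the design would give if the window ran from the first sample. The shift is always downward. It is negligible when few first draws are late or change is fast, and reaches one to two percentage points only when most or all are late and change is slower.

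**The case against.** The strongest reply is that the overlap is permitted but may hardly occur. The default is a draw before discharge, the two weeks are an allowance, and SAP 5.8 places the venipuncture on Day 1. If first draws fall on the day of enrolment, every gap is 14 to 42 days and there is no bias. A site would also have little reason to take a second sample on the day of the first, and 4.3 does require the second to follow the first. The substudy is site-specific, and actual draw dates could be handled in the analysis. All of this stands. It limits the likely size but does not close the gap in the rule.

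Three stronger readings are tempting, and the documents do not support them.

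- **That repeatability will look better than it is.** This needs enough late first draws paired with early second draws, and neither frequency is given.
- **That a large share of pairs is near-simultaneous at assay precision.** Pooling 20% or 40% of pairs at a CV of 1.9% with the rest at 10% gives √(0.2 × 1.9² + 0.8 × 10²) = 9.0% or √(0.4 × 1.9² + 0.6 × 10²) = 7.8%. Yet even if every first draw fell on day 14 and second draws were uniform, only 3/28 = 11% of pairs would be within 3 days. The 1.9% comes from duplicate determinations in blood from 3 subjects, not from two separate phlebotomies shipped to a core laboratory. The assumed 10% also lacks support: Protocol 2.3 cites an average change below 10% in 248 patients with cardiovascular disease retested at 6 to 52 weeks.
- **That the bias could carry the result under a 10% limit.** The figure in 4.3 is a background expectation from healthy subjects. It is not stated as a CV, and no acceptance limit is attached to it.

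**Conclusion.** The point holds as a defect of the sampling rule. Compliant pairs may be 0 to 42 days apart, while Protocol 4.3 frames repeatability over 14 to 42 days between tests. That follows from the text and needs no assumption.

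The effect is conditional. If variation between samples grows with time, as the protocol's own reasoning implies, short gaps bias the estimate towards repeatability, so stability over 2 to 6 weeks may be overstated. The size cannot be derived from the documents. It is nil with all first draws on the day of enrolment and small with few late ones. The tabulated CVs are illustrations under an assumed 10% biological CV, assumed time constants and uniform second draws; they are not estimates for this study. The change is worth making because it is cheap and the present rule admits pairs that cannot answer the substudy's question.

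**What to change.** **Protocol 1.1, 1.3 (note d) and 4.3:** count the 2-to-6-week window for the second sample from the date of the first FcγRIIa sample instead of from enrolment. Record both draw dates.

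**SAP:** base the main agreement analysis on pairs at least 14 days apart by actual draw dates. Show all pairs by actual gap as a sensitivity analysis. If second draws are already complete, this step alone deals with the problem.

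While editing, reconcile SAP 5.2 and 5.8 with the protocol. They describe Day 1 as the only in-person visit and the venipuncture as taking place on that day, which fits neither a late first draw nor the substudy draw.

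**Cost:** wording changes in the site-specific amendment and a short SAP paragraph, with no extra draw. With a first draw on day 14, the second could fall as late as day 14 + 42 = 56, two weeks later than now. Where the window cannot be moved, a few short-gap pairs leave the main analysis.

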## 5 STUDY POPULATION

Subjects meeting all the inclusion criteria and none of the exclusion criteria are eligible for enrollment into the study.

### 5.1 INCLUSION CRITERIA

1. Male or female subjects  $\geq$  18 years of age hospitalized with confirmed type 1 MI (STEMI or NSTEMI), referred to as the index event (described in Appendix 1).
2. Must have  $\geq$  2 of the following risk factors:
  - a) Age  $\geq$  65
  - b) Multi-vessel coronary artery disease (MVD) defined as  $\geq$ 2 vessels or left main with a stenosis  $\geq$ 50%
  - c) Chronic kidney disease (CKD) defined as estimated glomerular filtration rate (GFR)  $<$  60 ml/min/1.73 m^2
  - d) Diabetes mellitus (DM)
  - e) Prior MI
3. Must agree to participate in the study, to comply with all study procedures and follow-up contact
4. Signed the informed consent form

### 5.2 EXCLUSION CRITERIA

1. Participation in another trial in which the subject is known to receive or could receive anticoagulant or antiplatelet treatment as part of the trial intervention.
2. Non-cardiovascular conditions that, in the judgment of the investigator, will limit survival to less than 2 years

### 5.3 SCREEN FAILURES

Subjects who do not meet the criteria for participation in this study (screen failure) may not be rescreened during the same hospital admission period. The reason for the screen failure should be recorded in the site study log.

### 5.4 RECRUITMENT

Efforts will be made to enroll an ethnically diverse cohort with appropriate representation from women.

## 6 STUDY INTERVENTION

There is no study intervention. Treatment decisions are entirely at the discretion of the subject's health care provider.

### 6.1 MEDICATIONS

Anti-thrombotic therapy will be recorded in the case report form (CRF).

## 7 SUBJECT DISCONTINUATION/WITHDRAWAL FROM THE STUDY

Subjects are free to withdraw from participation in the study at any time upon request. The reason for subject discontinuation or withdrawal from the study will be recorded on the CRF.

### 7.1 LOST TO FOLLOW-UP

Every effort will be made to minimize the number of subjects who are lost to follow-up. The following actions must be taken if a subject misses a required study visit:

- The site will attempt to contact the subject and reschedule the missed visit and counsel the subject on the importance of maintaining the assigned visit schedule and ascertain if the subject wishes to and/or should continue in the study.
- Before a subject is deemed lost to follow-up, the investigator or designee will make every effort to regain contact with the subject (3 telephone calls and, if necessary, a certified letter to the subject's last known mailing address or local equivalent methods). These contact attempts should be documented in the subject's medical record or study file.
- Should the subject continue to be unreachable, he or she will be considered to have withdrawn from the study with a primary reason of lost to follow-up.
- Electronic medical records may be used to assess vital status (alive or dead) at the end of the study provided the subject has not withdrawn consent for follow-up.

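### Protocol 7.1 classes a subject as withdrawn after one missed 6-monthly visit and failed re-contact, with no rule to try again and no described route to non-fatal events

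*Protocol*

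**What the plan says.** Follow-up is by telephone. The schedule of activities (Protocol 1.3) has a "Telephone Study Visit every 6 months (+/- 4 weeks"), plus a final call.

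Protocol 7.1 sets out what happens when a visit is missed:

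- Trigger: "The following actions must be taken if a subject misses a required study visit". One missed visit is enough.
- First step: "The site will attempt to contact the subject and reschedule the missed visit".
- Before a subject is deemed lost: "3 telephone calls and, if necessary, a certified letter to the" last known address, or a local equivalent, with the attempts documented.
- If that fails: "Should the subject continue to be unreachable, he or she will be considered to have withdrawn from the study", with loss to follow-up as the reason.
- Back-up: "Electronic medical records may be used to assess vital status (alive or dead) at the end of the study", provided consent for follow-up still stands.

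Protocol 4.1 says "All subjects will be contacted at the end of the study for a final telephone visit", and on the use of records, "Medical records will be reviewed to confirm subject reported endpoints".

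SAP 5.3 allows public records as a further source, again for vital status only, and tabulates five measures of completeness of follow-up. The primary Cox model (SAP 5.7.1) censors at the end of complete follow-up. One sensitivity analysis censors instead at the end of vital-status follow-up.

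**The concern.** Being unreachable is not the same as withdrawing consent, and 7.1 itself separates the two when it allows record checks. Even so, it gives the unreachable subject the status of a withdrawn one. It sets no minimum time or number of missed visits, no instruction to try at the next scheduled call, and no rule for a subject who reappears. A later answered call could cover the whole gap, because MI, stroke and bleeding are found by asking the subject. Section 4.1 promises everyone a final call but does not say whether that includes subjects already classed as withdrawn, so sites may act differently.

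For a subject who stays unreached, the described record checks can show only whether the subject is alive or dead. A non-fatal primary event or a BARC 2-5 bleed has no described route into the data. At stake are avoidably lost events and follow-up time. There would also be bias if the events themselves make subjects hard to reach, for example after a disabling stroke.

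**Working it through.** The documents state no loss or dropout rate, so there is no plan figure to reproduce. What follows is an illustration.

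**Inputs from the documents.** 800 subjects and a minimum of 80 events (Protocol 9.2); about 12 months of enrolment and a 10% annual event rate (4.1); at least 18 months after the last enrolment (4.2); calls every 6 months plus a final call (1.3).

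**Assumptions.** Uniform enrolment, so follow-up runs from 1.5 to 2.5 years. Constant hazard. A proportion q of visits ends in failed re-contact *after the whole 7.1 sequence*, with q = 2% to 5%, at random. Any first event after the last successful contact is lost, deaths included.

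**1. Events with full follow-up.** λ = −ln(0.9) = 0.1054 per year.

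Expected first events = 800 × [1 − (0.9^1.5 − 0.9^2.5)/λ] = 800 × [1 − (0.8538 − 0.7684)/0.1054] ≈ 151.7. (Rounding the hazard to 0.105 gives 151.2.)

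By interval between calls: 41.1, 38.9, 36.9, 26.4 and 8.4.

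**2. Follow-up stops at the first failed re-contact.** An event in interval k is captured only if all k calls succeed, so captured events = Σ eₖ(1 − q)ᵏ.

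- q = 2%: 40.2 + 37.4 + 34.8 + 24.3 + 7.6 = 144.3, so 7.4 are lost.
- q = 5%: 39.0 + 35.1 + 31.7 + 21.5 + 6.5 = 133.8, so 17.9 are lost.

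By simulation, about 9% to 21% of subjects are lost before the end, with about 5% to 12% of person-time.

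**3. Calling continues, and the next answered call covers the gap** (simulation):

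| Chance of missing the next call after a miss | Events recovered, q = 2% | Events recovered, q = 5% |
|---|---|---|
| q (independent misses) | all but about 0.3 | all but about 1 |
| 80% | about 3 | about 7.5 |
| 90% | about 1.6 | about 4 |
| 100% | 0 | 0 |

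Someone who has not responded to three calls and a letter is unlikely to be as easy to reach next time as anyone else, so the independent case is a best case. The 80% and 90% figures are also assumed.

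**4. Does this loss bias rates?** Not when it is random. The simulated event rate is about 0.105 per person-year in every row, with or without withdrawal. Random loss costs precision only.

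**5. If loss depends on outcome (all rates assumed).** Take four 6-month intervals, with loss per call of 3% to 5% without an event and 10% to 20% after a non-fatal event. Let 30% to 50% of events be fatal, and let deaths within the interval be found. Then 122 to 138 of 152 events are captured, so 9% to 20% are missed. With 3% loss at every call regardless of outcome, about 6% are missed.

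**6. Event target.** The lowest figure above, 122, is well clear of 80.

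**The case against.** A reader might infer more than the text supports, in four ways.

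- *A single unanswered call removes a subject.* It does not. Rescheduling, three calls and, if necessary, a letter come first. A missed visit that is made good loses nothing.
- *Later contact is ruled out.* No passage forbids it, and 4.1 can be read as requiring a final call. But 7.1 assigns withdrawn status, and a site following it has no instruction to call again. The two sections need one rule.
- *The plan ignores loss to follow-up.* It does not. SAP 5.3 adds public records and the completeness tables, and 5.7.1 has the vital-status sensitivity analysis. These help only in part. The tables measure loss but recover nothing. The sensitivity analysis can add deaths only, and it counts the unobserved time as free of MI and stroke. A death found in records after complete follow-up ends appears to fall outside the primary model.
- *Event rates and negative predictive value will be distorted.* Under the planned censoring, random loss does not bias rates. An inflated negative predictive value would need outcome-related loss, or a calculation that counts censored subjects as event-free. The documents show neither. The size and direction of any bias in the FcγRIIa hazard ratio cannot be derived from them.

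It is also fair to object that the gain from continued calling is uncertain. That stands, and the table shows how far it falls when unreachability persists.

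**Conclusion.** The point holds as a defect in the follow-up rule, not as a demonstrated bias. Section 7.1 gives withdrawn status to subjects who have not withdrawn consent, provides no further attempts, and leaves non-fatal events in these subjects without a described route to detection. If 2% to 5% of visits end in failed re-contact, about 7 to 18 of roughly 152 first events are lost. Continued calling would return between about 2 and nearly all of these, depending on how persistent unreachability is; with 80% to 90% persistence it is about 2 to 8. Every rate here is assumed, because the documents give none.

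The 80-event minimum is not at risk. Outcome-related loss is clinically plausible and the planned analyses would reveal it only in part, but nothing in the documents shows that it will occur. The change is worth making because it is cheap and because non-fatal events are harder to recover once the study has closed.

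**What to change.** **Protocol 7.1 and 4.1.** Keep an unreachable subject who has not withdrawn consent on the call schedule. Attempt every later 6-monthly call and the final call, ask about the whole period since the last contact, and assign loss to follow-up only at study end. State in 4.1 that the final call includes these subjects.

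**Vital status.** Change the end-of-study check from *may* to *will*.

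**Record search for non-fatal events (optional).** If records are also searched for MI, stroke and BARC 2-5 bleeding, first confirm that consent allows it. Search for all unreached subjects whatever their FcγRIIa level. Site records can miss admissions elsewhere, so finding no event does not establish event-free follow-up. The SAP should therefore say that events found only in records, after complete follow-up ends, go into a sensitivity analysis unless complete follow-up to that date is established. Counting them without the matching follow-up time would itself bias the rates.

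**Cost.** A protocol amendment with IRB review, a short SAP addition, a few extra call attempts, and record look-ups for the subjects concerned. No new study visit.
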